2.2 Secondary Objective(s)

The secondary objectives of this study are:

- to evaluate the beneficial effect of Octagam 10% in subjects with active DM by assessing different parameters and scores at Week 16 and Week 40;
- to confirm the sustained benefit of treatment with Octagam 10% by assessing the primary response measures at Week 40;
- to evaluate the safety and tolerability of Octagam 10% in subjects with DM.

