To also include all data from the extension period in such Kaplan-Meier analyses, we will look at the abovementioned events and their timely relationship to the first infusion of Octagam.

To confirm the sustained benefit of treatment with Octagam 10%, response rates at Week 40 and changes from baseline to Week 40 will be presented descriptively (overall and by randomized treatment), including 95% confidence intervals.

Further details on the statistical presentations will be given in the SAP.

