3.1.2. Secondary Objectives

The secondary objectives of the study are:

- to evaluate the beneficial effect of Octagam 10% in patients with active DM by assessing different parameters and scores at Week 16 and Week 40;
- to confirm the sustained benefit of treatment with Octagam 10% by assessing the primary response measures also at Week 40;
- to evaluate the safety and tolerability of Octagam 10% in patients with DM.

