3.2.1. Primary Target Variables

The evaluation of the primary endpoint will be based on the newly developed Total Improvement Score (TIS), a scale from 0 to 100, with 20-39 points being minimal improvement, 40-59 points being moderate improvement, and ≥ 60 points being major improvement (Aggarwal et al., 2017, please refer to the protocol for details).

In the context of this study, subjects need to have at least minimal improvement at Week 16 (i.e. $TIS \geq 20$) to qualify as responders.

The primary endpoint is defined as the proportion of responders in the 2.0 g/kg Octagam 10% and placebo arms at Week 16, a responder being defined as a subject with an increase from baseline (Week 0) of ≥ 20 points on the Total Improvement Score (TIS) and who has not met "Confirmed Deterioration" criteria at 2 consecutive visits as defined in Section 8.4 up to (including) Week 16.

The TIS is based on the assessment of six core set measures (CSMs):

1. Physician Global Activity: Global Disease Activity (GDA), assessed by the investigator on a Visual Analog Scale (VAS)
2. Patient Global Activity: GDA, assessed by the patient on a VAS
3. Manual muscle testing: MMT-8 Muscle Grading and Testing
4. Health Assessment Questionnaire (HAQ): Standard HAQ used by the International Myositis Assessment and Clinical Studies Group (IMACS)
5. Enzymes: Aldolase, CK, ALAT, ASAT, LDH
6. Extra muscular activity: Evaluated as part of Myositis Disease Activity Assessment Tool [MDAAT]

Please refer to the protocol for further details and references on these CSMs. The CSMs will be assessed at Screening, at each visit of the first period, at Visit 9 (Week 28), and at the Termination Visit.

The TIS is calculated as a sum of sub-scores as detailed below. The level of improvement will always be based on the comparison of the current CSMs compared to the baseline (Week 0) values.

Core set measure	Level of improvement	Level score
Physician Global Activity	Worsening to 5% improvement	0
	>5% to 15% improvement	7,5
	>15% to 25% improvement	15
	>25% to 40% improvement	17,5
	>40% improvement	20
Patient Global Activity	Worsening to 5% improvement	0
	>5% to 15% improvement	2,5
	>15% to 25% improvement	5
	>25% to 40% improvement	7,5
	>40% improvement	10
Manual muscle testing (MMT)	Worsening to 2% improvement	0
	>2% to 10% improvement	10
	>10% to 20% improvement	20
	>20% to 30% improvement	27,5
	>30% improvement	32,5
Health Assessment Questionnaire (HAQ)	Worsening to 5% improvement	0

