5.1. Final Analyses and Reporting

As stated in section 4.1, this study consists of a double-blinded period, followed by an open-label extension period. The blind will however be maintained throughout the complete study to the extent possible; only for subjects who were switched during the first study period and show no further deterioration at Week 16 and for those subjects with confirmed deterioration at Week 16, the decision whether a subject is allowed to continue into the open-label period will imply whether the subject was initially treated with Octagam (Subject has to drop out) or Placebo (Subject continues). Otherwise the blind will not be broken before all subjects have completed the entire study and the final database has been locked and released for analysis according to the applicable standard operating procedures.

This process includes a data review, the identification and classification of any protocol deviations as detailed in section 7, and thus the subject disposition with respect to the analysis populations. All final, planned analyses identified in the protocol and in this SAP will be performed only after the last subject has completed the study, the subject disposition has been agreed and documented, and the final SAP has been approved.

Key statistics and study results will be made available to the study team following database lock and prior to completion of the final CSR by means of tables, figures and listings.

Any, post-hoc, exploratory analyses completed to support planned study analyses, which were not identified in the final SAP, will be documented and reported in the CSR or its appendices. Any results from such unplanned analyses will also be clearly identified in the text of the CSR.

No interim analysis is planned.

6. Sample Size Determination

The sample size calculation is based on the target parameters for the evaluation of the primary endpoint, i.e. the proportions of responders in the Octagam 10% and the placebo group at the end of the 16 week efficacy period (First Period).

A total sample size of 84 subjects is required to show a significant difference in the proportion of responders between Octagam and placebo group with a power of 80%, under the assumption that the true proportions of responders are 0.6 in the Octagam group and 0.3 in the placebo group. The sample size calculation is based on Pearson's chi square test using a two-sided alpha level of 0.05.

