In case the proportion of patients with missing values is greater than 10%, or if the modified ANCOVA detailed above gives a signal of divergence, the concerned data will be further reviewed and analyzed.

The time to at least minimal, at least moderate and major improvement in TIS, and the time to confirmed deterioration in the First Period and overall, will be summarized using based on Kaplan-Meier estimates that will also be presented graphically. For the analysis of improvement variables in the first period, the time to event will be censored at the time of switch to the alternate treatment group. A stratified log-rank test will be applied for time to event variables to compare both treatment groups. Cox regression models may be applied additionally to include randomization stratum and further baseline covariates in the analysis.

To also include all data from the extension period in such Kaplan-Meier analyses, we will look at the abovementioned events and their timely relationship to the first infusion of Octagam.

To confirm the sustained benefit of treatment with Octagam 10% , response rates at Week 40 and changes from baseline to Week 40 will be presented descriptively (overall and by randomized treatment), including 95% confidence intervals.

All individual core set measures (CSMs) used for the TIS, and all other efficacy endpoints will be analyzed and presented in full detail by means of descriptive statistics, including summary and frequency tables, as well as graphs according to the general principles described in sections 8 and 12.

The development of each CSM over time will be presented graphically.

The detailed list of all tables, figures and graphs, and the analysis populations used for each analysis will be provided in a separate document later, when all feedback from authorities will be available.

11. Safety and Tolerability Analyses

The safety analysis will comprise descriptive statistics, tabulations and listings of all treatment emergent adverse events (TEAEs), safety laboratory results, viral markers, vital signs, Wells' scores, Doppler scan results, and physical examination findings.

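### Sustained benefit is described only by marginal Week 40 results, which cannot show whether Week 16 responders kept their response

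*SAP*

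**What the plan says.** Protocol 2.2 sets a secondary objective "to confirm the sustained benefit of treatment with Octagam 10% by assessing the primary response measures at Week 40"; SAP 3.1.2 repeats it. The analysis assigned to it is one sentence in SAP 10.2, also found in Protocol 9.2.2: "response rates at Week 40 and changes from baseline to Week 40 will be presented descriptively (overall and by randomized treatment), including 95% confidence intervals". No test, threshold or success rule is attached.

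The component data exist at the visits that matter. SAP 3.2.1 states: "The CSMs will be assessed at Screening, at each visit of the first period, at Visit 9 (Week 28), and at the Termination Visit". TIS is always computed against Week 0, so response can be derived at Weeks 16, 28 and 40 for every subject assessed then.

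Other planned analyses also use Extension Period data (SAP 3.2.2 and 10.2): improvement categories at Week 40, mean TIS, changes in the individual core set measures and SF-36v2, CDASI change from Week 16 to Week 40, Kaplan-Meier time to improvement and to confirmed deterioration, and graphs of each core set measure over time. The list of tables is deferred to a separate document (SAP 10.2 and 13).

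**The concern.** In its natural sense, sustained means that subjects who had a benefit kept it. A response rate at one visit counts whoever responds then. New responders can replace subjects who lost response, and the rate does not move.

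None of the other planned analyses fills this gap:

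- Time to improvement measures onset, not persistence.
- Confirmed deterioration is judged against Week 0 (Protocol 4.3.1, SAP 8.4), so a subject can fall below TIS 20 without meeting it. It also needs two consecutive visits, and scheduled core set measures in the Extension Period fall only at Weeks 28 and 40.
- Protocol 7.2.1 notes that TIS cannot tell a stable subject from a worsening one.
- The only planned Week 16 to Week 40 change is in CDASI, a skin measure.
- Graphs of the core set measures do not tabulate retained response.

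The pooled rate has a further weakness. Placebo-randomised subjects who did not deteriorate first receive Octagam at Week 16. Those switched earlier had confirmed deterioration and are Week 16 non-responders by definition. Neither group has a Week 16 response on Octagam to sustain.

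At stake is what the Extension Period can say about durability, at a stage when the dose may be reduced from Week 28 and concomitant therapy tapered (Protocol 3.2 and 4.2.1).

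**Working it through.** **Inputs.** Response rates 0.6 (Octagam) and 0.3 (placebo), two-sided alpha 0.05, 80% power, Pearson chi-square, N = 84, and planned enrolment of 94 (SAP 6, Protocol 9.1). With 1:1 allocation, 94/2 = 47 per arm. The documents give no Week 40 rate, so it is an assumption and is varied below.

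**1. The plan's own figure.** With p̄ = 0.45, n per arm = [1.960·√(2·0.45·0.55) + 0.842·√(0.6·0.4 + 0.3·0.7)]² / 0.3² = (1.379 + 0.565)² / 0.09 ≈ 42, so N = 84. The stated size reproduces. Power at 47 per arm is 84.4%.

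**2. Expected Week 16 counts.** Octagam: 0.6 × 47 = 28.2, about 28 responders and 19 non-responders. Placebo: 0.3 × 47 = 14.1, about 14 responders.

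**3. What an unchanged Week 40 rate allows.** Let R16 and R40 be the responder counts among n subjects. The number responding at both visits lies between max(0, R16 + R40 − n) and min(R16, R40). With R16 = R40 = 28 and n = 47, the minimum is 28 + 28 − 47 = 9 and the maximum is 28. If c of the 19 non-responders become responders, 28 − c are retained:

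| New responders c | Retained | Planned display |
|---|---|---|
| 0 | 28/28 (100%) | 28/47 = 59.6% |
| 5 | 23/28 (82%) | 28/47 = 59.6% |
| 10 | 18/28 (64%) | 28/47 = 59.6% |
| 19 | 9/28 (32%) | 28/47 = 59.6% |

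The exact 95% CI on the planned display, 44.3% to 73.6%, is the same in every row.

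**4. How far the worst case reaches.** The last row needs all 19 non-responders to convert.

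- By Week 40 count: at 32/47 (68%) at least 28 + 32 − 47 = 13 are retained, so at most 15/28 (54%) are lost. At 33/47 (70%) at least 14 are retained, so at most 14/28 (50%) are lost. At 35/47 at most 12/28 (43%) are lost.
- By departures: if d of the 19 leave, at most 19 − d can convert, so with Week 40 at 28/47 at least 9 + d are retained. For d = 4 at most 15/28 (54%) are lost; for d = 5 at most 14/28 (50%).

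**5. The pooled rate.** Expected Week 16 responders are 28 + 14 = 42 of 94. With 56/94 (60%) responding at Week 40, as few as 42 + 56 − 94 = 4 need be the same subjects. With 47/94 or fewer, possibly none.

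**6. Precision of a direct estimate.** On 28 Week 16 responders, exact 95% intervals are: 9/28, 16% to 52%; 20/28 (71%), 51% to 87%; 22/28 (79%), 59% to 92%; 28/28, 88% to 100%.

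**The case against.** The objective defines its own measure: benefit of treatment, assessed by the primary response measures at Week 40. A Week 40 rate by randomised arm meets that wording; persistence within subjects is a stricter reading that the documents do not spell out. This stands, and it means the plan is incomplete rather than contradictory.

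The Week 40 rate is not the only evidence. The same sentence also names changes from baseline, and SAP 8 commits to using all data collected under Octagam. Large-scale relapse would probably show in mean TIS, the core set measures or CDASI. This stands too, but none of those measures loss of TIS response.

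The by-arm display keeps the Octagam arm visible, so the pooling problem affects only the overall column.

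A retention proportion has faults of its own. It is uncontrolled. It selects on a noisy threshold, so regression to the mean can lower it. In the Extension Period it mixes doses and tapered concomitant therapy. These are good reasons not to make it the main estimate, but not reasons to omit it.

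The deferred table list might contain a cross-table. That cannot be known, and the SAP text does not call for one.

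**Conclusion.** The gap is real and limited. Marginal Week 40 results cannot separate persistence from turnover, and nothing in the SAP text conditions on Week 16 response. With 47 per arm, 60% response at Week 16 and an unchanged Week 40 count, retention is undetermined between 32% and 100%. The lower end is an arithmetic bound, not a forecast. Mid-range values such as 64% or 82% need no extreme assumption and are equally invisible.

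A reader might infer that the plan tests sustained benefit and could declare the objective met after most responders had relapsed. The documents do not support that. The Week 40 results are descriptive, with no decision rule; the only success criterion is the Week 16 comparison in SAP 10.1. Loss of more than half is also ruled out at 33/47 or more, or at 28/47 once 5 or more non-responders have left. Some departures follow from the design: Octagam-randomised subjects switched after confirmed deterioration do not enter the Extension Period (Protocol 3.2), and those who discontinue before Week 16 count as non-responders (SAP 10.1).

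**What to change.** In SAP 10.2, keep the Week 40 rates by randomised arm and add a supportive descriptive analysis:

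1. A Week 16 by Week 40 responder/non-responder table for each randomised arm.
2. The proportion of Octagam-randomised Week 16 responders still responding at Week 28 and at Week 40, with exact 95% CI.
3. A rule that subjects who discontinue, or have no TIS at the visit in question, count as not sustained. This matches the Week 16 rule in SAP 9.2 and 10.1. For later visits the documents settle only drop-out after confirmed deterioration (Protocol 3.2); they state no explicit rule for other discontinuations or a missing Week 40 TIS.
4. A statement that the pooled overall rate will not be used as evidence of sustained benefit.

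The cost is SAP wording and a small amount of output from data already collected. The denominator falls to about 28, the interval widens, and the figure may look less favourable than the marginal rate. The report should state the limits given above: no control group, regression to the mean, and mixed dose and concomitant therapy.

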Subjects originally **randomized to Octagam 10%** who deteriorate at 2 consecutive visits in the First Period and who were subsequently switched to placebo will drop-out after the response assessment at Week 16 and will not enter the Extension Period.

Subjects dropping out due to confirmed deterioration at 2 consecutive visits will in any case be classified as non-responders in the statistical analysis.

Any subject deteriorating at 2 consecutive visits in the Extension Period will drop-out, independent of the initially assigned treatment arm and the Octagam 10% dose administered.

Figure 1 depicts the study design.

Figure 1: Scheme of Study Design

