4.3 Withdrawal and Replacement of Subjects

4.3.1 Premature Subject Withdrawal

Subjects have the right to withdraw from the study at any time for any reason, without the need to justify their decision. The Investigator also has the right to withdraw subjects from the study in case of AEs, poor compliance, or other reasons. Since an excessive rate of withdrawal can render the study non-interpretable, the unnecessary withdrawal of subjects must be avoided.

For any discontinuation after study entry, the Investigator will obtain all the required details and document the reason(s) for discontinuation in the eCRF. If the reason for withdrawal of a subject is an AE, the main specific event or laboratory test will be recorded in the eCRF, and the Investigator will make thorough efforts to clearly document the outcome.

Should a subject decide to withdraw, the Investigator will make the best efforts to complete and report the observations. The Investigator will document the reason(s) for withdrawal of each subject in the eCRF.

Subjects who terminate the study prematurely are drop-outs. The Investigator has to organize the Drop-out visit which is identical to the Termination visit procedures.

At Week 16, certain subjects have to drop-out, especially in case of (further) confirmed deterioration after the switch to the alternate treatment option. Please see Figure 1 for details.

Other reasons for premature termination of subjects may be:

- 1. Withdrawal of subject's consent.
- 2. Deterioration of DM (during Extension Period).
- 3. Pregnant subjects will be immediately excluded from the study.

- Investigator's opinion that the subject may be severely harmed if he/she continues trial participation, namely by the treatment and procedures according to the study protocol.
- 5. Occurrence of a disease which interferes with the study treatment or represents an exclusion criterion.
- 6. Administration of IGIV other than Octagam 10%.

"Confirmed deterioration" is essentially defined as follows according to Oddis et al. 2013 with a slight adaptation as agreed with the study's Steering Committee (excluding enzymes, which will not immediately be available for the evaluation of deterioration): [20]

• Physician's Global Disease Activity VAS worsening ≥ 2 cm and MMT-8 worsening ≥ 20% on 2 consecutive visits,

or

• global extra-muscular activity worsening ≥2 cm on the MDAAT VAS on 2 consecutive visits,

or

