8.3. Handling of Missing Data

In general, missing data will not be imputed, with a few exceptions. For ANCOVA analysis of changes from baseline to week 16, LOCF will be used in main model in case of missing values (e.g. due to early termination) and in case of switch to the alternate treatment group (as values obtained after the switch will not be included in the analysis).

For missing weight measurements the last available body weight will be used for all calculations related to dosing; in individual patient data listings missing data will however not be replaced by imputed values.

No analyses of the patterns of missing data will be done.

For adverse events the following will be applied:

An Adverse Event (AE) is defined as treatment-emergent, if first onset or worsening is after start of the first infusion of Octagam 10% or placebo.

If the start date and time of an AE are partially or completely missing, the AE will be assumed to be treatment-emergent if it cannot be definitely shown that the AE did not occur or worsen during the treatment emergent period (worst case approach). Missing dates and times will not be replaced.

For medications the following will be applied: A medication will be assumed to be concomitant if it cannot be definitely shown that the medication was not administered during the treatment period as defined in section 8.4 below. Missing dates will not be replaced.

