10.2. Secondary efficacy endpoints

All secondary efficacy endpoints will be analyzed and presented in full detail by means of descriptive statistics and inferential analyses as appropriate.

For TIS response at Week 16 by improvement category, the proportion of subjects with at least moderate improvement and the proportion of subjects with major improvement will be calculated together with subject counts and the associated 2-sided 95% confidence interval (CI) for the difference in the proportion of patients with improvement. Moreover, both treatment groups will be compared using a Cochran-Mantel Haenszel test, analogously as for the primary endpoint. The proportion of subjects in each treatment arm who meet confirmed deterioration criteria up to (including) Week 16 will be presented in the same way.

All mean changes to be evaluated as secondary endpoints (listed in section 3.2.2) will be presented by a full set of descriptive parameters: number of subjects with non-missing values, mean, standard deviation, median, minimum and maximum, 1st and 3rd quartile, 95% CI. Moreover, for all continuous secondary endpoints, an analysis of covariance (ANCOVA) will be used to analyze changes from baseline to Week 16. For patients who are switched to the alternate treatment before Week 16, the last value prior to switch will be carried forward to Week 16 and used to calculate change from baseline to Week 16. The model will include treatment and global disease activity as a fixed factor. Center will be included as random factor. The baseline value of the variable to be analyzed will be included as a covariate. Least square means will be derived and presented together with 95%-confidence intervals by treatment group. Moreover, two-sided 95% confidence intervals will be derived for the overall difference in least square means between Octagam and placebo treatment. As sensitivity analysis, a modified ANCOVA model will be used, where the changes from baseline to Week 16 are calculated based on Week 16 values, even if a patient is switched to the alternate

treatment before Week 16. To incorporate the switch into the model, the variable crossover (yes/no) which indicates if there was a switch to the alternate treatment will be included as additional factor into the ANCOVA model, as well as the treatment-by-cross-over interaction term.

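### Week 40 mean changes have no missing-data rule although deterioration forces exit, so the means meant to confirm sustained benefit are likely to look too favourable

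*SAP*

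**What the plan says.** Confirming sustained benefit at Week 40 is a secondary objective (Protocol 2.2, SAP 3.1.2). The planned evidence on levels is in SAP 10.2, repeated in Protocol 9.2.2: "response rates at Week 40 and changes from baseline to Week 40 will be presented descriptively (overall and by randomized treatment"), with 95% confidence intervals.

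The descriptive set for mean changes in SAP 10.2 begins with "number of subjects with non-missing values, mean, standard deviation, median, minimum and maximum", so it rests on observed values. SAP 8.3 states: "In general, missing data will not be imputed, with a few exceptions". The one efficacy exception there is: "For ANCOVA analysis of changes from baseline to week 16, LOCF will be used in main model in case of missing values". The same section rules out any analysis of missing-data patterns.

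Exit is tied to failure. Protocol 3.2 says: "Any subject deteriorating at 2 consecutive visits in the Extension Period will drop-out, independent of the initially assigned treatment arm". For the arm randomized to Octagam it adds that those "who deteriorate at 2 consecutive visits in the First Period and who were subsequently switched to placebo will drop-out after the response assessment"; the assessment meant is the Week 16 one. SAP 4.1 agrees and treats Week 16 as the termination visit of those who do not continue. SAP section 7 removes values obtained after a First Period switch from the by-visit tables.

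An exit assessment is collected. Protocol 4.3.1 says: "The Investigator has to organize the Drop-out visit which is identical to the Termination visit procedures". Protocol 6.1.10 lists SF-36v2, CSM and CDASI for it.

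**The concern.** A mean over the subjects still present describes the treated population only if leaving is unrelated to outcome. Here one route out is, by protocol, confirmed deterioration. The subjects most likely to lack a Week 40 value are those in whom benefit was not sustained, and sustained benefit is what the summary is meant to confirm. At Week 16 the SAP deals with this through carry-forward and an explicit non-responder rule. At Week 40 it has no matching rule for continuous endpoints.

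At stake is how the Week 40 means and their confidence intervals are read in the study report. There is no concurrent control at Week 40, because everyone remaining has received Octagam. The issue is therefore the level of an uncontrolled mean, not a treatment comparison.

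**Working it through.** **1. The plan's own figure.** The documents state no figure for Week 40. Their only planning calculation is the total of 84 for the Week 16 responder comparison (Protocol 9.1, SAP section 6: 0.6 versus 0.3, two-sided alpha 0.05, power 80%, 1:1). Per arm:

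n = [1.960 × √(2 × 0.45 × 0.55) + 0.842 × √(0.6 × 0.4 + 0.3 × 0.7)]² / 0.3² = (1.379 + 0.565)² / 0.09 ≈ 42

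The total is 84, which reproduces. Enrolling 94 leaves a margin of 10/94 = 10.6%, but that margin concerns the Week 16 endpoint. It gives no Week 40 drop-out rate.

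**2. Rules side by side.**

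| | Week 16 | Week 40 |
|---|---|---|
| Mean change, value missing | LOCF in the main ANCOVA (SAP 8.3) | none stated |
| Mean change, switched subject | last pre-switch value carried forward (SAP 10.2) | none stated |
| Response, deterioration drop-out | non-responder (SAP 10.1) | non-responder in any case (Protocol 3.2) |
| Response, other discontinuation or no score | non-responder (SAP 9.2, 10.1) | none stated |
| Percentage denominator | whole analysis population (SAP section 8) | same default |

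The gap is in the mean-change rows, plus one response row.

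**3. Who lacks a Week 40 value.**
- *Octagam subjects switched to placebo in the First Period.* They leave after Week 16. Their exit assessment follows the switch, and SAP section 7 excludes such values from by-visit tables. They have no usable Week 40 value even if exit visits are mapped to Week 40.
- *Octagam subjects whose deterioration is confirmed at Week 16 itself.* They also leave. They would have a Week 40 value only if their Week 16 record were relabelled.
- *Placebo subjects switched to Octagam who deteriorate again.* They leave at Week 16 (Protocol 3.2).
- *Extension Period deteriorators.* CSM are scheduled after Week 16 only at Week 28 and Termination (SAP 3.2.1). A Week 28 plus Week 40 confirmation still yields a Week 40 value. An exit before Week 40 needs Week 16 plus Week 28, or unscheduled visits, so these exits may be few.
- *Subjects who leave for other reasons.* No rule.

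**4. Size.** Let d be the share without a Week 40 value, mC the mean change in completers and mL the mean change in leavers, with improvement positive.

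All-subject mean = (1 − d) × mC + d × mL

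Overstatement = mC − all-subject mean = d × (mC − mL)

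The identity is exact, but d, mC and mL are not in the documents. All inputs below are assumptions. For TIS, mC = 40 is assumed, with mL = 0 (the floor of the scale) or 20.

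| d | TIS, mL = 0 | TIS, mL = 20 | gap 0.5 SD | gap 1 SD | gap 1.5 SD |
|---|---|---|---|---|---|
| 5% | 2.0 points | 1.0 | 0.025 SD | 0.05 SD | 0.075 SD |
| 10% | 4.0 | 2.0 | 0.05 | 0.10 | 0.15 |
| 20% | 8.0 | 4.0 | 0.10 | 0.20 | 0.30 |
| 30% | 12.0 | 6.0 | 0.15 | 0.30 | 0.45 |

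**The case against.** A reader might infer that the exit data are thrown away and that all Week 40 evidence comes from survivors. The documents do not support that.

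- **Exit data.** Nothing says Drop-out values are unused. The flowchart gives Week 40 termination and drop-out one shared column, Protocol 6.1.10 describes them together, and SAP 8.2 keeps withdrawn subjects wherever they contribute data. The accurate statement is that the mapping is undefined. This stands for Extension drop-outs. It does not rescue Octagam subjects switched to placebo, for the reason in step 3.
- **Response rates.** It is tempting to convert a 60% completer response into 0.6 × 0.9 = 54% or 0.6 × 0.8 = 48% of all subjects. The default whole-population denominator avoids that problem, and deterioration drop-outs are non-responders without a Week 16 limit. What remains is the missing rule for other discontinuations.
- **Other evidence.** Kaplan-Meier estimates of time to confirmed deterioration overall, including extension data, count the failures, and the n beside each mean makes attrition visible. Both help interpretation, but neither corrects a mean.
- **Missing-data trigger.** SAP 10.2 promises further review if more than 10% of values are missing. It follows the Week 16 ANCOVA text and names no method.
- **Later document.** SAP 10.2 leaves the population for each table to a separate list. That could settle the denominator, but not how a missing value is handled.
- **Weight.** The summary is secondary, descriptive and uncontrolled, and forced Extension exits may be few. Both points are fair and limit the importance of the finding.

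**Conclusion.** The point holds for Week 40 mean changes. Followed as written, the SAP gives observed-case means with no Week 40 missing-data rule, in a study where confirmed deterioration removes subjects. The means are likely to look too favourable, by d × (completer change − leaver change). With d of 10 to 20% and a 1 SD gap, both assumed, that is 0.1 to 0.2 SD. The direction rests on leavers having done worse than completers, which the exit rules make likely but do not guarantee, since some subjects leave for other reasons. The true size cannot be derived from the documents.

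The point does not extend to the Week 40 response rates as a whole, to the time-to-deterioration analysis, or to the primary Week 16 test. The text should be settled before database lock, since it concerns a stated objective and needs no new data.

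**What to change.** In SAP 10.2, for Week 40:

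1. Keep the observed-case means and show the n contributing. State whether Drop-out visit values enter them.
2. Beside them, add a summary in all FAS subjects treated with Octagam, using the last on-Octagam assessment where there is no Week 40 value. That is the Drop-out visit value if the subject was still on Octagam, or the last pre-switch value if the subject had been switched to placebo. The two are not interchangeable, because the exit value of a switched subject was obtained on placebo.
3. State that subjects without a Week 40 TIS for any reason, or with confirmed deterioration on Octagam, count as Week 40 non-responders in the FAS.

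Two details need a sentence each. SF-36v2 is scheduled only at Week 0, Week 16 and Termination/Drop-out, so a subject switched to placebo before Week 16 has only the Week 0 value before the switch, and carrying it forward gives zero change. For CDASI from Week 16, a carried value gives zero change for anyone who left at Week 16, so the change from Week 0 should be shown too.

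The cost is a few sentences, one more row per table and probably slightly less favourable Week 40 figures. Carry-forward also keeps early favourable values for subjects who leave for reasons other than failure, so neither summary is sufficient alone and both should be shown.
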